- 4.1. Participants will be recruited from the patient population at the clinics of [name], [name], [name] and [name], PA-C at the University of New Mexico’s Orthopaedic Department. Since all potential participants will be independently seeking care for osteoarthritis, the participating clinicians and research staff will screen the patients for inclusion criteria during their standard examination. Qualifying patients will be offered enrollment into the study at that time.
- 4.2. Inclusion criteria include being the age of eighteen or older, diagnosed symptomatic knee osteoarthritis, and radiographic evidence of knee osteoarthritis. For the purposes of this study, radiographic evidence of knee osteoarthritis is defined as any one or more of the following: osteophytes, joint space narrowing, loss of articular cartilage thickness, subchondral sclerosis or cysts. Patients will also meet inclusion criteria if their intake sheet pain score is at least a 3 out of 10, as pain scores less than 3 are unlikely to show a clinically meaningful improvement from any treatment option. Patients will be excluded from the study if they have a history of treatment with any intra-articular knee injection or have current ligament instability as demonstrated by a positive Lachman Test, Anterior or Posterior Drawer Test, or positive Valgus or Varus Stress Test.¹⁹ Patients with a known allergy to lidocaine will also be excluded from the study. Patients will be excluded if they do not meet our above-mentioned severity criteria with a pain score of at least 3 on the intake sheet.
- 4.3. This study will only include English or Spanish speaking adults over the age of eighteen who are capable of independently consenting to participate in a research study. This study will not include any children, pregnant women, or prisoners. Women of childbearing age will be included only after they have had a negative urine pregnancy test at point of care.
- 4.4. Individuals under the age of 18 will be excluded from this study. As osteoarthritis is largely considered a degenerative joint disease, this population is highly unlikely to have osteoarthritis of the knee and thus will not be eligible for the study.

5. Number of Subjects

- 5.1. This study will take place solely at the University of New Mexico Hospital.
- 5.2. Based on our power analysis, we need 75 participants to complete the study. All subjects will have been pre-screened for eligibility by the participating clinicians.

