- Individuals who agree to participate in this study will be enrolled during an initial screening visit which they will have independently sought and scheduled. Their participation will involve one procedure visit, two brief follow-up visits, and three online completion of surveys. We anticipate that it will take approximately 15 months from date of enrollment to complete each individual subject’s procedure and follow-up visits, allowing time for flexibility in scheduling based on the clinician and subject’s schedules.
- We estimate that it should take approximately three months to enroll 75 subjects. We anticipate this being feasible based on the four participating clinicians’ current schedules. Roughly, an orthopaedic surgeon may see upwards of 50 patients a day. Approximately 10% of these patients have knee OA and potentially qualify for the study.

PROTOCOL TITLE: “Evaluating the efficacy of micro-fragmented adipose tissue and intra-articular corticosteroid injections for symptomatic knee osteoarthritis: a randomized, placebo controlled study”

- *We anticipate the data analysis to take a maximum of two months following the completion of all data collection.*

7. Study Endpoints

- 7.1. *This study will conclude once all active, enrolled participants have completed their one-year follow-up.*
- 7.2. *Participants will be followed via standard of care and monitored at follow-up appointments. After we have had 10 participants enrolled in each group, we will do a preliminary evaluation of the available data.*
- 7.3. *Not applicable. We will not have exploratory endings.*

8. Research Setting

- 8.1. *Research will be conducted at the University of New Mexico Hospital Orthopaedic Clinics of [name], [name], [name] and [name], PA-C. Research, including all patient visits and procedures, will also be conducted at the CTSC.*
- 8.2. *Participants will be recruited from the patient population at the clinics of [name], [name], [name] and [name], PA-C at the University of New Mexico’s Orthopaedic Department. Since all potential participants will be independently seeking care for osteoarthritis, the participating clinicians and research staff will screen the patients for inclusion criteria during their standard examination.*
- 8.3. *Procedures and follow-up visits will be performed at the CTSC facilities on North Campus.*
- 8.4. *Not applicable. There will be no community advisory board*

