1. Participants will be screened prior to enrollment. Depending on their medical history and prior consultations, they will likely have a physical exam and x-rays of the affected knee(s). This is standard of care and will happen prior to enrollment in the study. X-ray images and medical data from these visits may be used for the purposes of analyzing statistical data.

PROTOCOL TITLE: "Evaluating the efficacy of micro-fragmented adipose tissue and intra-articular corticosteroid injections for symptomatic knee osteoarthritis: a randomized, placebo controlled study"

2. Upon enrollment, participants will be randomized to a treatment group and scheduled for their injection procedure.
3. At their injection visit, participants will complete the Western Ontario and McMaster Universities Osteoarthritis Index, a Visual Analog pain scale, and the Knee Injury and Osteoarthritis Outcome Score scales to establish a baseline. They will also fill out a medication log to document any medications that they take, including oral pain medications, although we will not be intervening with oral medications. They will complete these surveys and the log again at 2 weeks, 6 weeks, 3 months, 6 months, and 1 year after the injections

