Intra-articular knee injections, such as corticosteroids and Lipogems®, are employed in routine clinical practice for the treatment of knee osteoarthritis. With any injection, there is a risk of local adverse reaction such as pain or swelling, and a risk of infection. In addition to an injection, Lipogems® requires a lipoaspiration procedure from the patient's abdomen. Some risks of lipoaspiration include seromas and hematomas requiring drainage, infections, changes to the skin including hyperpigmentation, scarring, or induration. Very rarely, more serious complications (including skin necrosis or local anesthetic toxicity) may arise.^{24,25}

18.2. *We have received input from a board certified plastic surgeon on the risks of lipoaspiration. We have also reviewed the existing literature. Corticosteroid injection is part of the standard of care for treating knee osteoarthritis. As Lipogems® is still a relatively new treatment option, there may be unforeseen risks.*

18.3. *Patients who are pregnant will not be eligible for participation. Patients must verbally confirm they are not pregnant prior to enrollment in the study and prior to receiving their injection.*

18.4. *Not applicable. There are no risks to others who are not subjects.*

PROTOCOL TITLE: "Evaluating the efficacy of micro-fragmented adipose tissue and intra-articular corticosteroid injections for symptomatic knee osteoarthritis: a randomized, placebo controlled study"

18.5. To minimize risk, all injections will be performed following standard of care sterile techniques and treatment guidelines. We will have a board certified plastic surgeon trained in lipoaspiration train the study investigators accordingly. To protect patient confidentiality, we will take the necessary precautions to protect patient data. All electronic files will be password protected and stored on a password protected computer behind a locked door. All paper documents will be kept in a locked filing cabinet in a locked office.

19. Potential Benefits to Subjects

19.1. Potential benefits include the possibility of reduced pain and/or increased functionality of the affected knee after injection with Lipogems® or corticosteroids.

20. Recruitment Methods

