25.1.3. The study, possibly treatment outcomes, and follow-up requirements will be explicitly stated at the time of consent. The patient will be made aware of their standard of care treatment options and will also be invited to participate in the study. The consent process will emphasize that patients have the right to accept or deny entry into the study with no consequences on their care.

25.1.4. Potential subjects will be offered the choice to participate if they meet eligibility criteria at visits with their provider prior to enrollment in the

PROTOCOL TITLE: “Evaluating the efficacy of micro-fragmented adipose tissue and intra-articular corticosteroid injections for symptomatic knee osteoarthritis: a randomized, placebo controlled study”

study. The study will be explained at that time. If the patient is interested, informed consent will happen at that time.

- 25.1.5. *Patients will provide consent for participation prior to enrolling in the study. This consent covers the injection and all follow-up visits. At each visit, participants will be asked if they wish to continue in the study and will provide verbal consent.*
- 25.1.6. *During informed consent, the person obtaining consent will utilize teach-back and ask the patient to explain, in their own words, what the study entails and what they are consenting to.*
- 25.1.7. *People obtaining consent will utilize teach back to make sure that patients understood the study, what possible treatment outcomes are, and what follow-up is required of study participants.*

Subjects not fluent in English

- 25.1.8. *This study will also include Spanish speaking participants.*
- 25.1.9. *For informed consent, explanation of the study, and all visits thereafter, a translator will be available to translate for the patient and the clinician. The informed consent document will be translated to Spanish.*
- 25.1.10. *Not applicable. No short-form consent documents will be used. There will be one standard informed consent document that must be explained to the patient and read by the patient prior to enrollment.*

Cognitively Impaired Adults/Adults Unable to Consent/Use of a Legally Authorized Representative

- 25.1.11. *Not applicable. This study will only be enrolled individuals with full, independent ability to provide legally effective consent.*
- 25.1.12. *All subjects are required to have full, independent ability to provide legally effective consent.*

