- 25.1.13. *During the consent process, those obtaining consent will utilize teach-back to ensure that the individual understands what participation in the study entails. Individuals will be asked to explain, in their own words, what they are agreeing to before giving informed consent. For individuals who are Spanish speaking, an interpreter will be made available to help with the consent process. If an individual is unable to explain the study or verbalize what they are agreeing to, he/she will not be enrolled.*
- 25.1.14. *As above, teach-back and asking the individuals to explain what their agreement to participate entails will be utilized during the consent process to ensure that individuals understand the study prior to providing informed consent. The research staff member obtaining consent are responsible for confirming that an individual can provide consent.*

PROTOCOL TITLE: “Evaluating the efficacy of micro-fragmented adipose tissue and intra-articular corticosteroid injections for symptomatic knee osteoarthritis: a randomized, placebo controlled study”

Research staff members will document this process by signing their respective portion of the informed consent document.

- 25.1.15. *The participant’s decisional capacity will be assessed at each visit (procedure, where consent is given, and four follow-up exams) by the participating clinicians.*
- 25.1.16. *Not applicable. Patients will have full capacity to provide consent prior to enrolling in the study.*
- 25.1.17. *Not applicable. This study will only enroll participants who can independently give informed consent.*
- 25.1.18. *Not applicable. No research will be conducted outside of New Mexico for this study.*
- 25.1.19. *Not applicable. Consent to participate in this study must be given by the participant.*
- 25.1.20. *Not applicable. If a patient is unable to provide informed consent they will be excluded from the study.*

Subjects who are not yet adults (infants, children, teenagers)

- 25.1.21. *Not applicable. No individuals under the age of 18 will be enrolled in this study.*
- 25.1.22. *Verification of patient’s date of birth will allow selection of participants over the age of eighteen.*
- 25.1.23. *Not applicable. No parental permission will be obtained as all study participants are required to be eighteen years of age or older and capable of providing independent, legally effective consent.*
Describe whether parental permission will be obtained from:

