- 29.1. Not applicable. The study does not involve individuals who are vulnerable to coercion or undue influence.

30. Community-Based Participatory Research

- 30.1. Not applicable. There will not be any community involvement in this study.

31. Research Involving American Indian/Native Populations

- 31.1. This is neither an inclusion or exclusion criteria for the study. Participants will be offered the chance to participate and the study will be explained at length to potential participants. Participants are free to decline the study if would prefer not to participate. They will continue to receive the standard of care.

32. Transnational Research

- 32.1. Not applicable. Our study will not involve transnational research.

33. Drugs or Devices

- 33.1. All drugs and devices are approved and cleared by the FDA.

Lipogems® (brand name: Lipogems System, manufacturer: Lipogems International S.p.A., no generic currently on the market) device kits will be sent to [name] at the University of New Mexico Hospital after a participant has enrolled in the study and been randomly assigned to receive

PROTOCOL TITLE: “*Evaluating the efficacy of micro-fragmented adipose tissue and intra-articular corticosteroid injections for symptomatic knee osteoarthritis: a randomized, placebo controlled study*”

Lipogems®. Treatment drugs and devices will be stored, handled, and dispensed by a licensed pharmacist at UNM IDS Pharmacy. Drugs will be stored under proper conditions of sanitation, temperature, light, moisture, ventilation, segregation, safety, and security. These items will be stored in accordance with existing hospital policy and storage requirements. [name], [name], and [name] will be authorized to perform Lipogems procedures. [name], [name], [name] and [name], PA-C are authorized to give corticosteroid or placebo injections.

33.2. *Not applicable. No drugs or devices in this study are investigational. They are all marketed and none are being used off-label.*

33.3. *Not applicable.*

PROTOCOL TITLE: “*Evaluating the efficacy of micro-fragmented adipose tissue and intra-articular corticosteroid injections for symptomatic knee osteoarthritis: a randomized, placebo controlled study*”

Checklist Section

This section contains checklists to provide information on a variety of topics that require special determinations by the IRB. Please complete all checklists relevant to your research.

I. Waivers or Alterations of Consent, Assent, and HIPAA Authorization

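### The pregnancy test is tied to inclusion at the screening visit; on the later injection day the only stated check is verbal.

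*Combined protocol and SAP*

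**What the plan says.** Two sections deal with pregnancy. Section 4.3 excludes pregnant women and makes a test a condition of entry: "Women of childbearing age will be included only after they have had a negative urine pregnancy test at point of care". Section 18.3 adds self-report at two points: "Patients must verbally confirm they are not pregnant prior to enrollment in the study and prior to receiving their injection".

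The order of events comes from other sections:

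- **Enrollment.** 4.1 has patients screened at their standard examination and offered enrollment then. 6.1 agrees: "Individuals who agree to participate in this study will be enrolled during an initial screening visit which they will have independently sought and scheduled".
- **Consent.** 25.1.4 places it at the same visit: "If the patient is interested, informed consent will happen at that time".
- **Randomization and scheduling.** 12.1 item 2: "Upon enrollment, participants will be randomized to a treatment group and scheduled for their injection procedure".
- **Procedure.** 6.1 counts it as a visit of its own: "Their participation will involve one procedure visit, two brief follow-up visits, and three online completion of surveys".
- **Lipogems kit.** Under 33.1 the kit is sent "after a participant has enrolled in the study and been randomly assigned to receive" that treatment.

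One parenthesis in 25.1.15 reads differently. It lists the visits as "procedure, where consent is given, and four follow-up exams", which would put consent at the procedure.

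**The concern.** The test protects against exposure during pregnancy, and that exposure occurs at the procedure. Under 12.1 item 4 it is 80 mg triamcinolone with lidocaine in one arm and abdominal lipoaspiration followed by injection in another. A test tied to enrollment shows the woman's status at enrollment. If pregnancy begins or becomes detectable after that, the remaining safeguard is her own statement, which cannot reveal a pregnancy she does not know about.

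By requiring a urine test for inclusion, the plan itself treats self-report as insufficient at that step. It then relies on self-report at the step where the risk arises. Section 14.5 adds that safety data are not collected, so a missed pregnancy has no defined place in the study data, although 22.4 does require adverse events to be reported.

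What is at stake is participant safety. Randomization, sample size, power and the planned models are unaffected.

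**Working it through.** The plan gives no figure for this point, so there is none to reproduce. The check is a reading of the visit sequence, followed by two rough sizes.

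**Visit sequence**

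| Step | Where stated | Pregnancy check stated |
|---|---|---|
| Screening, consent, enrollment | 4.1, 6.1, 25.1.4 | Urine test before inclusion (4.3); verbal (18.3) |
| Randomization and scheduling | 12.1 item 2 | None |
| Kit sent, Lipogems arm | 33.1 | None |
| Questionnaires and medication log at the injection visit | 12.1 item 3 | None |
| Injection, or lipoaspiration plus injection | 12.1 item 4 | Verbal (18.3) |

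1. Section 4.3 names no visit. The test must precede inclusion, and inclusion takes place at the screening visit under 4.1, 6.1 and 25.1.4. The link to screening is therefore an inference, but it rests on several consistent sections.
2. Section 12.1 sets out to list all research procedures in time order. The steps for the injection visit are questionnaires, a medication log and the injection. No pregnancy test appears there or in the cost table in 22.1.
3. Section 18.3 is the only text that ties a pregnancy check to the injection, and that check is verbal.
4. No section sets a maximum interval between test and injection.

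**Interval between test and injection**

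- Enrollment to completion: about 15 months (6.1).
- Injection to last questionnaire: 12 months (12.1 item 3).
- Slack: 15 − 12 = 3 months.

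This slack also has to absorb late follow-up, and the 15 months is itself approximate. About 3 months is thus an upper limit implied by the timeline, and the usual gap is probably shorter. The lower limit is above zero in the Lipogems arm because of the kit, and could be near zero in the other two arms.

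**Number of women (assumption)**

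The documents do not give the expected number of women of childbearing age. Section 2.3 gives 1.7 million adults under 45 and 6.6 million aged 45–64 with osteoarthritis. Taking under 45 as a stand-in for childbearing age:

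- Share under 45 among those under 65: 1.7 / (1.7 + 6.6) = 0.205.
- Applied to 75 participants: 0.205 × 75 = 15.4 people of both sexes.
- If half are women: 15.4 × 0.5 = 7.7, or about 8.
- In the two active arms: 7.7 × 2/3 = 5.1, or about 5.

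If every participant under 45 were a woman, the figure would be about 15. Counting participants over 65 lowers all of these; counting women in their late forties as of childbearing age raises them somewhat. The chance that one of these women becomes pregnant between visits without knowing it cannot be derived from the documents.

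**The case against.** The best counter-argument is that 4.3 names no visit. A test at the point of care could mean the place and day of treatment, and the parenthesis in 25.1.15 lends this some support. On that reading the test may already fall on the procedure day. The gaps in 12.1 and 22.1 do not settle it: the screening step in 12.1 item 1 omits the test too, so the lists show only that the test was left out altogether.

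The second argument is that three layers already exist: pregnant women are ineligible, a negative test is required, and verbal confirmation is repeated before injection. A second test would then be a stricter choice among acceptable ones. The enforced gap concerns only one arm, the numbers are small, and nothing in the documents quantifies fetal risk.

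Some of this stands. The visit for the test is inferred, silence in the lists is weak evidence, and the expected number of affected women is low. The main point survives. Testing at the procedure would place an entry criterion after randomization and contradict 6.1, 12.1 item 2 and 25.1.4; a single parenthesis does not outweigh those. If day-of-injection testing is what was meant, the plan still needs to say so. The layers also do not overlap where it matters: the objective test belongs to enrollment, while the exposure is covered by self-report alone.

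**Conclusion.** The concern holds. Followed as written, the plan allows triamcinolone with lidocaine, or lipoaspiration plus injection, to be given on the strength of an earlier test of unstated age and a verbal statement. Sections 4.3 and 18.3 do not contradict each other; the fault is timing.

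The scale is small: about 8 women across three arms, given the national age mix in 2.3 and an equal sex split, with an interval that is above zero in the Lipogems arm and at most about 3 months. The conclusion does not depend on these estimates. It rests on the visit sequence and on the absence of any injection-day test in the protocol; the consent form (22.5) and drug attachment (10.4) were not available for checking. The change should be made because it closes a participant-safety gap at very little cost.

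**What to change.** Require a negative point-of-care urine test on the day of injection, before lipoaspiration or injection, for every woman of childbearing age in all three arms. Testing every arm alike also avoids giving corticosteroid and placebo participants a clue to their assignment. Four places need wording:

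- **4.3:** *included only after a negative urine pregnancy test at point of care, and injected only after a negative test on the day of injection; a positive test means no injection.* If enrollment and injection fall on the same day, one test serves both.
- **12.1:** list the test between items 3 and 4.
- **18.3:** state that verbal confirmation is in addition to the test.
- **22.1:** add a row for the test, paid by the study.

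The cost is at most one more urine test per woman of childbearing age, of a kind the plan already uses. A woman who tests positive on the day would be randomized but not treated, which should be rare.
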